2.8.2 Deaths

Separate summaries and listings will be provided for deaths for each treatment period.

The number of deaths resulting from SAEs suspected to be related to study treatment and SAEs irrespective of study treatment relationship will be provided by SOC and PT.

2.8.3 Laboratory data

The summary of laboratory evaluations will be presented for three groups of laboratory tests (hematology, chemistry and urinalysis). In addition to the individual laboratory parameters the ratios “total cholesterol / HDL” and “apolipoprotein B / apolipoprotein A1” will be derived and summarized.

For urinalysis, frequency tables will be presented.

Descriptive summary statistics for the change from baseline to each study visit will be presented. These descriptive summaries will be presented by laboratory test and treatment group. Change from baseline will only be summarized for patients with both baseline and post baseline values and will be calculated as:

$$\text{change from baseline} = \text{post baseline value} - \text{baseline value}$$

For each parameter, the maximum change from baseline within each study period will be analyzed analogously.

QuantiFERON TB-Gold test will also be analyzed by the central laboratory.

In addition, shift tables will be provided for all parameters to compare a patient's baseline laboratory evaluation relative to the visit's observed value. For the shift tables, the normal laboratory ranges will be used to evaluate whether a particular laboratory test value was normal, low, or high for each visit value relative to whether or not the baseline value was normal, low, or high. Also the shifts to the most extreme laboratory test value within a treatment period will be presented as well (including category “high and low”). These summaries will be presented by laboratory test and treatment group.

The following laboratory parameters will be analyzed with respect to numerical Common Terminology Criteria for Adverse Events (CTCAE) grades, given in Table 2.8-2: hemoglobin, platelets, white blood cell count, neutrophils, lymphocytes, creatinine, total bilirubin (TBL), gamma-glutamyl transferase (GGT), alanine aminotransferase (ALT), aspartate aminotransferase (AST), alkaline phosphatase (ALP), glucose, cholesterol, triglycerides (TG).

These summaries will be split into hematology and chemistry for study level reports and the pooled summary of clinical safety.

Table 2.8-1 CTCAE grades for laboratory parameters to be analyzed

CTCAE Term	Grade 1	Grade 2	Grade 3	Grade 4
HGB decreased (Anemia)	<LLN – 100 g/L	<100 – 80 g/L	<80 g/L	
Platelet count Decreased	<LLN – 75.0 x10e9 /L	<75.0 - 50.0 x10e9 /L	<50.0 – 25.0 x10e9 /L	<25.0 x 10e9 /L
White blood cell Decreased	<LLN - 3.0 x 10e9 /L	<3.0 - 2.0 x 10e9 /L	<2.0 - 1.0 x 10e9 /L	<1.0 x 10e9 /L
Neutrophil count Decreased	<LLN - 1.5 x 10e9 /L	<1.5 - 1.0 x 10e9 /L	<1.0 - 0.5 x 10e9 /L	<0.5 x 10e9 /L
Lymphocyte count Decreased	<LLN - 0.8 x 10e9/L	<0.8 - 0.5 x 10e9 /L	<0.5 - 0.2 x 10e9 /L	<0.2 x 10e9 /L

		>1.5 - 3.0 x baseline;		
Creatinine increased*	>1 - 1.5 x baseline; >ULN - 1.5 x ULN	>1.5 - 3.0 xULN	>3.0 baseline; >3.0 - 6.0 x ULN	>6.0 x ULN
TBL increased	>ULN - 1.5 x ULN	>1.5 - 3.0 x ULN	>3.0 - 10.0 x ULN	>10.0 x ULN
GGT increased	>ULN - 2.5 x ULN	>2.5 - 5.0 x ULN	>5.0 - 20.0 x ULN	>20.0 x ULN
ALT increased	>ULN - 3.0 x ULN	>3.0 - 5.0 x ULN	>5.0 - 20.0 x ULN	>20.0 x ULN
AST increased	>ULN - 3.0 x ULN	>3.0 - 5.0 x ULN	>5.0 - 20.0 x ULN	>20.0 x ULN
ALP increased	>ULN - 2.5 x ULN	>2.5 - 5.0 x ULN	>5.0 - 20.0 x ULN	>20.0 x ULN
Glucose increased (Hyperglycemia)	>ULN - 8.9 mmol/L	>8.9 - 13.9 mmol/L	>13.9 - 27.8 mmol/L	>27.8 mmol/L
Glucose decreased (Hypoglycemia)	<LLN - 3.0 mmol/L	<3.0 - 2.2 mmol/L 7.75 - 10.34	<2.2 - 1.7 mmol/L	<1.7 mmol/L
Cholesterol high Hypertriglycerid emia	>ULN - 7.75 mmol/L 1.71 - 3.42 mmol/L	mmol/L >3.42 - 5.7mmol/L	>10.34 - 12.92 mmol/L >5.7 - 11.4 mmol/L	>12.92 mmol/L >11.4 mmol/L

*Note: for "creatinine increased" the baseline criteria do not apply

Shift tables will be presented comparing baseline laboratory result (CTCAE grade) with the worst results (expressed in CTCAE grade) during the treatment phase (either initial or entire) analyzed. Of note, baseline will be defined as last assessment prior to first dosing in initial treatment phase. Patients with abnormal laboratory values will be listed and values outside the normal ranges will be flagged.

Summaries for newly occurring or worsening clinically notable lipid abnormalities will also be provided cumulatively for each of the following parameters and categories:

- HDL:
 - <=LLN
 - <0.8 x LLN
- LDL, cholesterol, triglycerides:
 - >=ULN
 - >1.5 x ULN
 - >2.5 x ULN

Newly occurring or worsening liver enzyme abnormalities will also be summarized based on the event criteria given in Table 2.8-3 below:

Table 2.8-2 Liver-related events

Parameter	Criterion
ALT	>3xULN; >5xULN; >8xULN; >10xULN, >20xULN
AST	>3xULN; >5xULN; >8xULN >10xULN; >20xULN
ALT or AST	>3xULN; >5xULN; >8xULN >10xULN; >20xULN
TBL	>1.5xULN, >2xULN, >3xULN,

ALP	>2xULN, >3xULN, >5xULN
ALT or AST & TBL	ALT or AST >3xULN & TBL >2xULN; ALT or AST >5xULN & TBL >2xULN; ALT or AST >8xULN & TBL >2xULN; ALT or AST >10xULN & TBL >2xULN
ALP & TBL	ALP >3xULN & TBL >2xULN ALP >5xULN & TBL >2xULN
ALT or AST & TBL & ALP	ALT or AST >3xULN & TBL >2xULN & ALP <2xULN (Hy's Law) Note: elevated ALP may suggest obstruction as a consequence of gall bladder or bile duct disease; ALP may also be increased in malignancy. FDA therefore terms Hy's Law cases as indicators of pure hepatocellular injury. This does not mean that cases of ALT or AST >3xULN & TBL >2xULN & ALP \geq 2xULN may not result in severe DILI.

Notes:

In studies which enroll patients with pre-existing liver disease, baseline LFT may be increased above ULN; in such a case it is meaningful to add the condition “and worse than baseline” to the abnormality Criteria

For a combined criterion to be fulfilled, all conditions have to be fulfilled on the same visit. The criteria are not mutually exclusive, e.g. a subject with ALT = 6.42xULN is counted for ALT >3xULN and ALT>5x ULN.

Individual subject data listings will be provided for patients with abnormal laboratory data. Data of patients with newly occurring or worsening liver enzyme abnormalities will be listed in an additional listing.

Separate summaries and listings will be provided for urine pregnancy results by visit for each treatment period.

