2.1.2 Visits windows

Visit-windows will be used for the data that is summarized by visit; they are based on the study evaluation schedule and comprise a set of days around the nominal visit day. For any assessment, there are the protocol defined scheduled visits around which visit windows were created to cover the complete range of days within the study. The visit windows are shown in [Table 2-1](#). These apply to measurements taken at every visit. For assessments, collected less often different visit windows will be applied as detailed below.

When visit windows are used, all visits will be re-aligned, i.e., they will be mapped into one of the visit windows. E.g., if the *Week 4* visit of a subject is delayed and occurs on Day 46 instead of on Day 29, say, it will be re-aligned to visit window *Week 8*. In the case of major deviations from the visit schedule, or due to unscheduled visits, several assessments of a subject may fall in a particular visit window (either scheduled or unscheduled). Statistical approaches to handle multiple assessments in a given visit window are specified below.

Of note, subjects are allowed to have gaps in visits.

Table 2-1 Assessment windows for scheduled visits

Analysis Visit	Week	Scheduled Day	Visit Window
Baseline	BSL	1	-28 days to Day 1*
Week 1	1	8	Day 2-11
Week 2	2	15	Day 12-18
Week 3	3	22	Day 19-25
Week 4	4	29	Day 26-43
Week 8	8	57	Day 44-71
Week 12	12	85	Day 72-104
Week 16	16	113	Day 105-141
Week 24	24	162	Day 142-183
Week 32	32	218	Day 184-253
Week 40	40	289	Day 254-323
Week 48	48	337	Day 324-351
Week 52	52	365	Day 352 onwards

* Baseline measurement before the first drug administration for safety assessments and before the randomization for efficacy assessments. For efficacy visit windows, refer to date of randomization.

For parameters, which are not collected at every visit (e.g., FACIT-Fatigue©, HAQ-DI©), visit windows defined in [Table 2-4](#) will be combined. For example, if a parameter is measured at Week 12 and Week 24 only, Week 12 visit window will extend from Day 2 to Day 104 (combining Week 1 to Week 12 visit windows), Week 24 will extend from Day 105 to Day 183 (combining Week 16 to Week 24). If more than one assessment falls into the interval, the rules defined in [Section 2.1.3](#) below are applied.

Table 2-4a Drug administration windows for scheduled visits of Exposure Data

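### Combined liver criteria count only same-visit elevations, so a bilirubin rise sampled after ALT/AST has fallen back to 3×ULN or below enters no ALT/AST-with-bilirubin or Hy's Law row

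*SAP*

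**What the plan says.** Section 2.8.3 introduces the liver table (Table 2.8-2) as follows: "Newly occurring or worsening liver enzyme abnormalities will also be summarized based on the event criteria". The table has three kinds of combined row:

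- ALT or AST with total bilirubin (TBL), in four steps ending with "ALT or AST >10xULN & TBL >2xULN". ALP plays no part here.
- ALP above 3× or 5×ULN with TBL above 2×ULN.
- The Hy's Law row, which needs three analytes: "ALT or AST >3xULN & TBL >2xULN & ALP <2xULN".

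The notes below the table give the timing rule: "For a combined criterion to be fulfilled, all conditions have to be fulfilled on the same visit". The SAP gives no time window and no second count for elevations seen at different visits. It also does not say whether a visit here means a sampling date or an analysis window. The distinction matters because section 2.1.2 re-aligns data to windows and accepts that "due to unscheduled visits, several assessments of a subject may fall in a particular visit window".

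The section also provides single-analyte rows for ALT, AST, TBL and ALP, worst-grade shift tables, and listings of abnormal values, including a separate one for liver abnormalities.

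**The concern.** The combined rows are the only place in the SAP where a transaminase elevation and a bilirubin elevation are joined within a patient and counted. No hepatic topic is among the adverse events of special interest in section 2.8.1.1, and the single-analyte rows do not show whether the same patient appears in both.

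Under the same-visit rule, a pair of elevations that was fully sampled can still be absent from the count if the bilirubin value came from a later visit. What is at stake is how the combined rows can be read. A zero in the Hy's Law row would mean that no patient met all cut-offs at one visit. It would not mean that no patient had both elevations. With 495 planned patients, a single such case would be of interest to a safety reader.

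**Working it through.** The SAP gives no figure for this point, so there is none to reproduce. The check applies the rule to example patients and reads the visit spacing from Table 2-1.

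**Step 1: the rule applied.** The values are invented multiples of ULN. The visits are scheduled visits from Table 2-1: Week 8 is Day 57 (window Day 44–71) and Week 12 is Day 85 (window Day 72–104). The two visits are distinct whether a visit means a date or a window.

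| Patient | Visit | ALT | TBL | ALP |
|---|---|---|---|---|
| A | Week 8 | 6.4 | 1.2 | 1.1 |
| A | Week 12 | 2.4 | 2.6 | 1.2 |
| B | Week 8 | 8.0 | 1.2 | 1.1 |
| B | Week 12 | 3.4 | 2.6 | 1.2 |

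- Patient A, Week 8: ALT 6.4 > 3, but TBL 1.2 is not above 2. Week 12: TBL 2.6 > 2, but ALT 2.4 is not above 3. No single visit meets both conditions, so A is in no ALT/AST-with-TBL row and not in the Hy's Law row. A does appear in the ALT >3× and >5×ULN rows and in the TBL >1.5× and >2×ULN rows.
- Patient B, Week 12: ALT 3.4 > 3, TBL 2.6 > 2, ALP 1.2 < 2. B is counted in the >3×ULN combined row and in the Hy's Law row.

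A later bilirubin rise is therefore lost only if ALT and AST are at 3×ULN or below when it is sampled.

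**Step 2: visit spacing.** Table 2-1 has Baseline and Weeks 1, 2, 3, 4, 8, 12, 16, 24, 32, 40, 48 and 52. The gaps in weeks are 1, 1, 1, 1, 4, 4, 4, 8, 8, 8, 8, 4.

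- 8-week gaps: 4 × 8 = 32 of 52 weeks (62%).
- Gaps of 4 weeks or more: 32 + 4 × 4 = 48 of 52 weeks (92%).
- In days: 4 × 7 = 28 and 8 × 7 = 56. This uses the week numbers. The scheduled days printed in Table 2-1 from Week 16 to Week 48 (113, 162, 218, 289, 337) imply gaps of 49, 56, 71 and 48 days.

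The SAP does not list the laboratory sampling visits, and section 2.1.2 allows for assessments not made at every visit: "For assessments, collected less often different visit windows will be applied as detailed below". Laboratory spacing equal to Table 2-1 is therefore an assumption.

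**Step 3: can ALT fall back between visits?** Assume ALT declines exponentially from a sampled peak with half-life h. The time it stays above 3×ULN is h × log2(peak / 3). The half-life is not in the SAP, so a range of 3 to 21 days is shown.

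| Peak (×ULN) | h = 3 d | h = 7 d | h = 14 d | h = 21 d |
|---|---|---|---|---|
| 5 | 2.2 | 5.2 | 10.3 | 15.5 |
| 8 | 4.2 | 9.9 | 19.8 | 29.7 |
| 10 | 5.2 | 12.2 | 24.3 | 36.5 |
| 20 | 8.2 | 19.2 | 38.3 | 57.5 |

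In 12 of these 16 cells ALT is back to 3×ULN within 28 days, and in 15 of 16 within 56 days. The cells are scenarios, not probabilities. They show only that patient A's pattern is plausible at this spacing. They say nothing about how often bilirubin rises late.

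**The case against.** The strongest reply is that nothing here is wrong or contradictory. The same-visit rule is clear and pre-specified, and no other SAP text conflicts with it. The single-analyte rows, shift tables and listings remain, and with very few patients a reviewer could read the liver listing one by one. This stands to a large extent. The point is a gap in what is counted, not an error. It does not remove the gap, because no output is defined to link the two elevations.

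Several stronger readings are tempting and are not supported:

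- A reader might infer that every combined row needs ALT/AST, TBL and ALP together. Only the Hy's Law row does.
- A reader might infer that any bilirubin rise after the transaminase peak is lost. Patient B shows it is counted while ALT or AST is still above 3×ULN.
- A reader might turn the 4- and 8-week gaps into a percentage of cases missed. That would measure sparse sampling. An episode that no sample caught is lost under any counting rule; this rule loses only pairs sampled on different occasions. Unscheduled samples may also narrow the gaps.
- A reader might take the note in the Hy's Law row as conflicting with the rule. That note concerns ALP at or above 2×ULN, not timing, and such patients still enter the ALT/AST-with-TBL rows.
- A reader might say the trial would declare itself free of Hy's Law cases. The SAP makes no such statement.

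**Conclusion.** The point holds in a limited form. Under section 2.8.3, a patient whose ALT or AST exceeds 3×ULN at one visit, and whose TBL exceeds 2×ULN only at a later visit with ALT and AST back to 3×ULN or below, is in no ALT/AST-with-TBL or Hy's Law row. This follows from the rule alone.

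The size cannot be derived from the SAP; 0 to a few patients is a judgement. That the pattern occurs at all rests on the premise that bilirubin can rise after transaminases have begun to fall, which is general clinical reasoning and not in the document. How readily it escapes the count depends on laboratory spacing resembling Table 2-1. The primary and key secondary analyses are unaffected. The change is worth making because it is cheap, but nothing in the trial's efficacy conclusions depends on it.

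The undefined meaning of a visit is a second, smaller defect in the same sentence. If it means an analysis window, values from different dates could be combined. The selection rule in section 2.1.3, which keeps the quantitative value closest to the visit, could also discard an unscheduled result before the criterion is applied.

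**What to change.** 1. Keep the existing same-visit rows, and state whether same visit means sampling date or analysis window.
2. Add non-concurrent rows to Table 2.8-2 for ALT/AST with TBL and for Hy's Law: TBL above 2×ULN on or after the date of ALT or AST above 3×ULN, within the same analysis period. For the Hy's Law row, require ALP below 2×ULN at the ALT/AST elevation. These rows include the same-visit cases that meet the definition, so the excess over the existing row is the information gained.
3. Use all scheduled and unscheduled post-baseline results for these rows.
4. If a time limit is preferred, it must span the 56-day gap between scheduled visits. A 30-day limit, for example, could not link two on-schedule visits 8 weeks apart.
5. State how a pair that straddles the Week 12 switch from placebo to secukinumab is attributed.
6. List each such patient with the dates of both elevations.

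The cost is a few table rows, one date comparison on data already collected, and one listing. The downside is that a few non-causal co-occurrences will appear, such as an unrelated benign bilirubin rise, and will need review from the listing.

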2.8.4 Other safety data

2.8.4.1 ECG and cardiac imaging data

The following quantitative variables will be summarized: RR interval, PR interval, QRS duration, QT interval, and Fridericia (QTcF) correction will be presented for QTc.

QTcF will summarized by computing the number and percentage of patients (including 95% confidence intervals for pooled analyses, e.g. DMC or SCS) with:

- QTcF > 500 msec
- QTcF > 480 msec
- QTcF > 450 msec
- QTcF changes from baseline > 30 msec
- QTcF changes from baseline > 60 msec
- PR > 250 msec

Summary statistics will be presented for ECG variables by visit and treatment group.

In addition, shift tables comparing baseline ECG interpretation (normal, abnormal, not available, total) with the worst on-study interpretation (normal, abnormal, not available, total) will be provided.

A listing of all newly occurring or worsening abnormalities will be provided, as well as a by subject listing of all quantitative ECG parameters.

2.8.4.2 Vital signs

Analysis in vital signs measurement using descriptive summary statistics for the change from baseline for each post-baseline visit will be performed. These descriptive summaries will be presented by vital sign and treatment group. Change from baseline will only be summarized for patients with both baseline and post-baseline values and will be calculated as:

$$\text{change from baseline} = \text{post-baseline value} - \text{baseline value}$$

The number and percentage of patients with newly occurring notable vital signs will be presented. Criteria for notable vital sign abnormalities are provided in Table 2.8-4 below.

Table 2.8-3 Criteria for notable vital sign abnormalities

Vital sign (unit)	Notable abnormalities
Systolic blood pressure (mmHg)	$\geq 140 \text{ mmHg}$ or $< 90 \text{ mmHg}$
Diastolic blood pressure (mmHg)	$\geq 90 \text{ mmHg}$ or $< 60 \text{ mmHg}$
Pulse (bpm)	$> 100 \text{ bpm}$ or $< 60 \text{ bpm}$

An overview of the safety analyses is described in Table 2.8-1 below.

Table 2.8-4 Overview of analyses on some safety endpoints

Analysis period	SAEs	AEs	Study drug related AEs	AESI	Notables for vitals/ECG/lab criteria
Day 1 – Week 12	
 • Crude rates • Exposure time adjusted incidence rates* 	
 • Crude rates • Exposure time adjusted incidence rates* 	
 • Crude rates 	
 • Crude rates • Exposure time adjusted incidence rates* 	
 • Crude rates
Entire Treatment (upto Week 52)	
 • Crude rates • Exposure time adjusted incidence rates* 	
 • Crude rates • Exposure time adjusted incidence rates* 	
 • Crude rates 	
 • Crude rates • Exposure time adjusted incidence rates* 	
 • Crude rates

*Exposure time adjusted incidence rates will be done for the following:

- at the PSOC level for all SAEs and all AEs
- at the preferred term level for
 - all SAEs and AESIs

- the common AEs, which are defined as at least 2% of the patients in the combined AIN457 groups during the initial treatment period or events that had an incidence rate of at least 5.0 cases per 100 subject-years in the combined AIN457 groups during the entire treatment period

2.9 Pharmacokinetic endpoints

Not Applicable.

2.10 PD and PK/PD analyses

Not Applicable.

2.11 Patient-reported outcomes

Variables related to health-related quality of life (HR-QoL) are described below. All HR-QoL variables will be evaluated based on FAS patients.

Physical function index (HAQ-DI[©])

The mean change from baseline of Physical function index (HAQ-DI[©]) at Week 12 will be analyzed by using an ANCOVA model with treatment group, visit and concomitant MTX intake status, as factors and baseline HAQ-DI index as continuous covariate. The adjusted (LS) mean difference will be calculated as a point estimate together with the corresponding 95% confidence interval and p-value.

FACIT-Fatigue[©] score

The mean change from baseline of FACIT-Fatigue[©] total score at Week 12 will be analyzed by using an ANCOVA model with treatment group, visit and concomitant MTX intake status, as factors and baseline FACIT-Fatigue score as continuous covariate. The adjusted (LS) mean difference will be calculated as a point estimate together with the corresponding 95% confidence interval and p-value.

[figure not shown]
ASAS Health Index

[figure not shown]
The mean change from baseline of ASAS health index at Week 12 will be analyzed by using an ANCOVA model with treatment group, visit and concomitant MTX intake status, as factors and baseline ASAS Health Index as continuous covariate. The adjusted (LS) mean difference will be calculated as a point estimate together with the corresponding 95% confidence interval and p-value.

[figure not shown]
Additionally, summary statistics will be provided for all the visits till Week 52 for all patient-reported outcomes. Graphical representation will also be performed if required.

[figure not shown]
2.12 Biomarkers

Not Applicable.

3 Sample size calculation

The selected criterion for the primary objective, the ASAS 20 score, is intended to be used in patients with axial skeleton involvement. Consequently, secukinumab data available from previous studies on this outcome measure, related to AS patients, can be taken into account. Compared to PsA patients, in AS patients the peripheral joints involvement is less pronounced. Thus, the ASAS 20 score for AS patients is expected to capture information entirely related to the axial skeleton involvement. Patients with PsA, who will be included in the present study, are characterized by concomitantly experiencing axial and peripheral joints disease. Thus, the ASAS 20 score is expected to also reflect the peripheral joints components.

To assume the magnitude of ASAS 20 response for PsA patients treated with secukinumab data from CAIN457F2310 (AS patients) and the CAIN457F2312 (PsA patients) have been considered.

The CAIN457F2310 study compared secukinumab to placebo in AS patients, and the ASAS 20 response rate at Week 12 was 57% for 150 mg secukinumab and 28% for placebo (300mg secukinumab was not tested). These results are a basis to extrapolate the expected results for the current study.

In a phase 3 study of Secukinumab in PsA patients, CAIN457F2312, the performance of 300 mg secukinumab is, compared to 150 mg secukinumab, numerically better in the achievement of the ACR 20 score. Assuming comparable trends in treatment response of the spine and the peripheral joints, a slightly different response between the 300 mg and the 150 mg treatment group was chosen. In addition, from data available in the literature ([Lubrano and Spadaro 2012](#)) it appears that the spinal involvement in PsA is milder compared to AS in terms of inflammation and impact on physical function, so that it can be expected that PsA patients might more easily achieve an ASAS20 score compared to AS patients. Similarly, we can assume that placebo response rates in AxPsA patients may be higher compared to AS.

[figure not shown]
For the 150 mg secukinumab treatment group a response rate of 57% is expected at Week 12.

For the 300 mg secukinumab treatment group a response rate of 60% is expected at Week 12.

An overall type I error (2-sided) 5% will be used to control type I error. Since two secukinumab doses will be tested versus placebo in a hierarchical manner, no type-I-error adjustment is required for each comparison with respect to the primary endpoint (ASAS 20 response at Week 12). To achieve 92% power and assuming conservatively a response rate of 40% in the placebo group, at least 150 patients per group would be needed under equal allocation to show a response rate of 60% in the secukinumab 300 mg group. Using the same number of patients per group, the second test will have at least 80% power to detect a difference, if the true response rates are 57% in secukinumab 150 mg group and 40% in placebo. The above sample size calculation is based on Fisher's exact test.

To compensate for drop-outs and protocol violations, 165 patients per group (=495 total) should be recruited into this trial.

SAS® version 9.4 software was used for the calculation of sample size.

5 Appendix

